10.2.1 Transcranial Direct Current Stimulation

Montage Set-up Protocol

The Soterix Medical bilateral M1 tDCS montage set-up protocol will be completed during all five sessions of the study. Participants will be sent instructional videos on how to perform the following procedures via REDCap. They will be asked to view these videos prior to the videoconferencing call on practice session 1. Participants will receive a mock device that does not have the ability to stimulate to allow them to practice setup with the instructional videos.

For all sessions: the lab team will press the "now" button on the survey to begin recording the time duration to place the tDCS headgear on the head appropriately. Parent Participants will be instructed to:

- 1) Connect the provided cables to the device using the banana plugs on the back of the device
- 2) Place the tDCS headgear on the child's head with the arrow aligned with the nose and upload an image of the step
- 3) Mark locations below the red and black markers with the provided pen/pencil
- 4) Use the provided alcohol pads to clean the skin at the marked locations and identify any redness, cuts, pimples, etc.
- 5) Insert the connector cord pin securely into the opening of the receptacle on the rubber insert
- 6) Snap on the two tDCS sponge pads saturated in saline to the red and black markers and upload an image.

Both the caregiver and the laboratory team will record the time these steps were completed.

Non-active Mock Device

Practice Day 1: Now, participants will be asked to leave the tDCS setup in place for 20 minutes. Caregivers will observe the child during this time to see if the electrode sponges move or if the child adjusts the headgear. After the 20 minutes, the caregiver will be instructed to mark the new location of the arrow and measure the distance the arrow may have moved during the 20 minutes. An adverse event survey will be conducted prior to the session, at the 10-minute mark, and post stimulation

Active Device – At least one safety monitor study team member is present in the home of the participant team

Sham Day 2: The study team staff will evaluate the tDCS montage set-up for successful set-up. If set-up is completed correctly, the caregiver will activate the tDCS device for a sham stimulation. Participants will receive 30 seconds current ramp-up to 1.5mA immediately followed by ramp-down back to 0. They will continue to wear the headgear with no stimulation until the end of the 20-minute session when the current will once again receive ramp up to 1.5mA immediately followed by 30 second ramp-down. This will allow the child to potentially experience the mild skin tingling in order to adjust and prepare for the active sessions. The level of stimulation will be adjusted if necessary. An adverse event survey will be conducted prior to the session, at the 10-minute mark, and post stimulation. Vitals (blood pressure, respiration rate, and heart rate) will also be taken before and after stimulation. The participant will be given the option to use an iPad to watch videos during the 20-minute session.

Active Days 3-5: Same as Day 2, except participants will receive 20 minutes of tDCS stimulation. Caregivers and the investigative team will observe the child during this time to see if the electrode sponges move or if the child adjusts the headgear. After the 20 minutes, the caregiver will be instructed to mark the new location of the arrow and measure the distance the arrow may have moved during the 20 minutes of stimulation. If the child were to experience a mild adverse event, the caregiver and study team staff will opt to stop the active stimulation, assess the event, discuss with the study Medical Monitor and reassess. If deemed appropriate by the Medical Monitor the laboratory investigative team would discuss the plan to move forward with the Participant Team and make adjustments to stimulation intensity for future sessions for comfort.

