3.0 STUDY SUMMARY

3.1 Synopsis

Full Title	Remotely Monitored Transcranial Direct Current Stimulation in Children with Cerebral Palsy
Short Title	Pediatric Brain and Movement
Protocol Number	[HS IRB]
ClinicalTrials.gov Identifier & Summary	This study is being performed to determine the safety, tolerability and feasibility of remotely monitored transcranial direct current stimulation for children with cerebral palsy.
Number of Site(s)	This study is being done at one site: The University of Wisconsin Madison.
Main Inclusion Criteria	
 Children with hemiparetic cerebral palsy with a radiologically confirmed perinatal brain bleed/stroke Ability to follow 2-step commands Aged between 8 years 0 days and 21 years.
Main Exclusion Criteria	
 Inaccessibility to internet and a working computer/laptop/device Neoplasm Presence of metal implants Epilepsy History of seizure within 2 years preceding the study
Objective(s)	
Primary Objective
 
 To assess safety and tolerability of remotely monitored tDCS using our safety survey and optional 6-month/12-month follow up 
Secondary Objectives
 
 To evaluate the quality, ease and comfort of in-home device set-up. To evaluate the quality of tDCS stimulation.
Endpoints	
Primary Endpoint
 
Adverse events survey (pre, during, and post stimulation on sessions 1-5) and Box and Blocks test (pre and post stimulation sessions 2-5) will assess possible adverse effects.
 
Secondary Endpoints
 
 Setup speed SMARTscan™ electrode contact quality
Study Design	This is an exploratory pilot open label trial that will assess the safety and feasibility of active tDCS in the home setting under caregiver and remote investigator supervision and direction, with a study safety monitor in the home on days when there is an active device present. An optional 6 month/12-month follow up session will be completed to to assess Box and Blocks scores and medical status since r participation in the primary study.

IND or IDE Number	Abbreviated IDE requirements apply for Non-Significant Risk Device
Study Intervention	Participants will receive 20 minutes of 1.5 mA transcranial direct current stimulation (tDCS) for three consecutive days.
Total Number of Subjects	A total of 10 subjects will be recruited.

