8.0 SUBJECT SELECTION

8.1 Inclusion & Exclusion Criteria

Inclusion Criteria

1. Aged between 8 years 0 days and 21 years 365 days

2. Children who have hemiparetic cerebral palsy with a history of perinatal brain bleed/stroke
3. Receptive language function to follow two-step commands
4. Able to give informed assent along with the informed consent of the legal guardian. If the participant is 18-21 (with the capacity to consent), they must be able to give informed consent.
5. Intentional about representing the sub-population of children with CP who experience intellectual disability (at least 2/10 participants with mild intellectual disabilities will be recruited)
6. ≥ 10 degrees of active motion at the metacarpophalangeal joint
7. Children who have had surgeries, which may influence motor function e.g.- tendon transfer, will be included, yet surgical history will be documented and included in any publication within a participant characteristics table.

Exclusion Criteria

1. Inaccessibility to internet and a working computer/laptop/device.
2. Implants
3. Neoplasm
4. Metabolic Disorders
5. Epilepsy
6. Seizure within two years preceding the study
7. Acquired Traumatic Brain Injury
8. Pregnancy
9. Indwelling metal or incompatible medical devices
10. Evidence of skin disease or skin abnormalities
11. Botulinum toxin or Phenol block within [six-months] preceding the study
12. Disorder of Cellular Migration and Proliferation

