10.2.5 Adverse events survey

Tolerance and report of any symptoms will be formally assessed using tDCS-specific participant safety questionnaires. This includes common mild effects like skin tingling and itching, as well as others such

as headache, anxiety and mood changes, or any other events. This survey is filled out before, during at the 10-minute mark, and after tDCS stimulation sessions 1-5.

10.2.6 1-week Follow-up

We will ask the participants an open-ended question to check-in, assess the family's experience with the overall procedure and potential interest in future studies. This will be called the tDCS tolerance survey. This will occur via telephone one week after completion of the session.

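### The electrode sites are checked for visible skin changes before each session, but no recorded inspection is described when the sponges come off, and session 5 has no later scheduled look

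*Combined protocol and SAP*

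**What the plan says.** **Before current.** Section 10.2.1 states that the "montage set-up protocol will be completed during all five sessions of the study". Step 4 of that set-up has the caregiver "Use the provided alcohol pads to clean the skin at the marked locations and identify any redness, cuts, pimples, etc". No recording of the result is described. Images are uploaded at steps 2 and 6, both before stimulation.

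**After current.** On active days, once the 20 minutes are over, "the caregiver will be instructed to mark the new location of the arrow and measure the distance the arrow may have moved". Section 10.2.3 adds vital signs taken by the safety monitor, section 10.2.4 the Box and Blocks test, and section 10.2.2 the ease and comfort survey. The calendar in section 10.1 and Figure 1 in section 7.1 list the same kinds of item and no skin check.

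**Adverse event survey.** Section 10.2.5 says: "Tolerance and report of any symptoms will be formally assessed using tDCS-specific participant safety questionnaires". On content: "This includes common mild effects like skin tingling and itching, as well as others such" as headache, anxiety and altered mood, with an open category for anything else. On timing: "This survey is filled out before, during at the 10-minute mark, and after tDCS stimulation sessions 1-5". The synopsis makes this survey part of the primary endpoint: "Adverse events survey (pre, during, and post stimulation on sessions 1-5) and Box and Blocks test (pre and post stimulation sessions 2-5".

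**After the last session.** Section 10.2.6 has a telephone contact one week later with an open-ended question.

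**The concern.** The protocol treats the visible state of the skin as worth checking before current is applied, but describes no paired observation afterwards. The pre-session look is a baseline without an outcome.

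The trial asks whether caregiver-placed electrodes at home are safe and tolerable. The planned analysis in section 3.1 compares the frequency of reported adverse events, as a percentage of participants enrolled, with published laboratory studies in which trained personnel gave the stimulation. A visible mark that nobody is asked to look for may go unrecorded, and the home figure would then be too low. The montage is over the motor cortex on both sides (section 9.1), so the sites are on the scalp, where the child cannot see them. Participants may be as young as 8, and at least 2 of 10 are to have mild intellectual disability (section 8.1). A survey item for other events can pick up a visible sign only if someone has looked.

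**Working it through.** The plan gives no figure to reproduce here. The check compares what is scheduled before and after current, counts sessions, and then illustrates the consequence under stated assumptions.

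**Inputs.** 10 participants (section 3.1); 3 active sessions each, on days 3 to 5 (section 7.1); set-up, and so step 4, in all 5 sessions (section 10.2.1); survey 3 times per session in sessions 1 to 5 (section 10.2.5).

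**Ways a visible skin change after active current could be recorded**

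- *Inspection at sponge removal:* none described.
- *Post-session survey:* solicited from every participant. There are 5 × 3 = 15 administrations per participant, 15 × 10 = 150 in all, of which 3 × 10 = 30 follow active sessions. The named skin items are tingling and itching; redness, burn or lesion is not named.
- *Safety monitor:* in the home for sessions 2 to 5. The only post-session measurement assigned is vital signs.
- *Next session's step 4:* available after sessions 3 and 4. It is nominally a day later, since sessions are on consecutive days (section 7.1), but section 8.7 tolerates completion within two weeks.
- *One-week telephone contact:* no visual check.

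**Session counts, if all 10 complete**

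- Active sessions: 10 × 3 = 30.
- With a described inspection at removal: 0 of 30.
- Followed by a later set-up check (sessions 3 and 4): 10 × 2 = 20 of 30.
- With no later scheduled look (session 5): 10 of 30, one third.

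**What incomplete capture would do at N = 10.** Let p be the true per-participant rate of a visible skin effect and s the share of cases recorded. The chance of recording at least one case is 1 − (1 − p·s)^10. Neither p nor s is in the documents; these values are assumptions.

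| p | s = 100% | s = 70% | s = 50% |
|---|---|---|---|
| 5% | 40.1% | 30.0% | 22.4% |
| 10% | 65.1% | 51.6% | 40.1% |
| 20% | 89.3% | 77.9% | 65.1% |

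For example, at p = 10%: 1 − 0.90^10 = 65.1% with full capture, against 1 − 0.95^10 = 40.1% with half captured.

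Even with full capture, 0 of 10 leaves a one-sided 95% upper bound of 1 − 0.05^(1/10) = 25.9% (two-sided Clopper-Pearson: 1 − 0.025^(1/10) = 30.8%). That bound presumes that cases are seen when they occur. With a denominator of 10, one missed participant moves a skin-specific rate by 10 percentage points. The frequency of any adverse event moves only if that participant reported nothing else.

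**The case against.** Four objections deserve an answer.

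**Safeguards exist.** A reader might infer that a skin injury would be recorded only if someone volunteered it. The documents do not support that. The survey is solicited before, during and after every session, asks about skin sensations and has an open item. A trained monitor is in the home for sessions 2 to 5, present purely for safety, and another team member is on video throughout (section 10.2). Section 10.8 has the study team, as well as the parent or adult participant, report events. Section 10.2.5 does not say who completes the survey, so it cannot be assumed to be the child alone. All of this stands. What remains is that none of these people is assigned to look at the skin and record it.

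**The skin is seen again.** A reader might also infer that it is never looked at after current. That is too strong, because step 4 in sessions 4 and 5 is a look at the same sites after sessions 3 and 4. The complete gap is session 5.

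**The text is incomplete.** The contents list session-by-session sections, known risks and adverse event definitions whose body is not in the text reviewed; section 10.3.7 breaks off mid-sentence; the survey items are not reproduced; and section 10.8 places full monitoring details in a separate plan. A skin check or a redness item could be in any of these, so absence from the whole plan is not established.

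**Exclusion 10.** It might seem that step 4 conflicts with the exclusion for "Evidence of skin disease or skin abnormalities". It does not. The exclusion governs enrolment and step 4 is a per-session check, while later changes fall under the discretionary withdrawal reasons in section 8.7.

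It is also fair to say that adding an inspection only at home could raise the home rate through better ascertainment and distort the comparison with published studies. That is accepted and shapes the fix.

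**Conclusion.** The point holds in a limited form. The text describes a look at both electrode sites before each session, no recorded inspection at sponge removal, and no visible sign among the named survey items. The gap at removal covers all 30 planned active sessions. For 20 of them a later set-up check partly compensates, though no record of it is described; for the 10 final sessions nothing scheduled does.

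This rests on all 10 participants completing three active sessions, and on the unseen survey items and sections not already supplying the check. The documents give no rate of skin effects and no basis for a capture share, so the probabilities above show how sensitive the result is; they do not estimate events missed. Nor can the documents show which way the comparison with laboratory studies is biased, because how those studies ascertained skin effects is not stated. This is a worthwhile low-cost improvement to safety capture in a small open-label pilot. It does not invalidate the design.

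**What to change.** In section 10.2.1, repeat the step 4 inspection at both marked sites when the sponges are removed, in all five sessions, and upload an image as is already done at steps 2 and 6. In section 10.2.5, add an item to the post-session survey for any finding that was absent at that day's pre-session check; this requires the pre-session result to be recorded too. Add the check to the calendar in section 10.1. Use session 1 (mock) and session 2 (sham) as each child's reference for marks left by sponges and straps.

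In the analysis, report inspection-detected findings separately from survey-reported events, and use only the latter in the comparison with published laboratory rates unless those studies are known to have inspected the skin. If a missing section or the survey form already contains such a check, a cross-reference from section 10.2.1 is enough.

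**Cost.** An estimated minute or two per session, one image and one REDCap item. Image upload and photo authorization are already in place. The monitor is in the home for sessions 2 to 5; in session 1 the caregiver would do it under video guidance. The downside is that harmless transient redness will be recorded, which the mock and sham days help to interpret. No stimulation setting or clinical rule changes.

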10.2.2 Setup ease/comfort survey

This survey will be completed at the end of all five sessions. The survey will evaluate the participant's overall experience of the session by addressing the following topics:

- Caregiver: - How difficult were the tDCS setup instructions to understand?
- Caregiver: - How could instructions be improved in the future?
- Child - How comfortable was wearing the tDCS cap and sponges?
- Child – How could we make wearing the cap more comfortable?
- Any general comments

10.2.3 Vitals

Blood pressure, heart rate, and respiration rate will be taken pre and post stimulation on days 2-5 to ensure participant safety and monitor any changes in vitals. The safety monitor will take all vital measurements. These will be recorded on REDCap.

10.2.4 Motor assessments – Box and Blocks Test

Hand motor function will be assessed as a control measure before and after stimulation on days 2-5 with the Box and Blocks test. Instructions to this task will be read directly to the participant during the videoconferencing call. The testing researcher will guide testing with the Box and Blocks test (wherein the child moves as many 1" wooden blocks within 1 minute). There will be 1 trial period and 4 subsequent tests of the dominant and non-dominant hand (2 tests per hand).

10.2.5 Adverse events survey

Tolerance and report of any symptoms will be formally assessed using tDCS-specific participant safety questionnaires. This includes common mild effects like skin tingling and itching, as well as others such

as headache, anxiety and mood changes, or any other events. This survey is filled out before, during at the 10-minute mark, and after tDCS stimulation sessions 1-5.

10.2.6 1-week Follow-up

We will ask the participants an open-ended question to check-in, assess the family's experience with the overall procedure and potential interest in future studies. This will be called the tDCS tolerance survey. This will occur via telephone one week after completion of the session.

10.2.7 Optional 6-month/12-month Follow-up

10.2.7.1 *Medical Records*

To conduct a medical record review and assess medical status and the potential for new onset seizures since participation in the primary study, we will obtain a consent for a standardized medical record release under the Health Insurance Portability and Accountability Act (HIPAA), provided the previous HIPAA consent for medical record release has not expired. Our goal is to collect medical records that reflect the participant's current medical status. We will obtain participant's most updated medical records to review their current health status and review any changes since participation in the primary study. We are more specifically looking for any key factors relevant to our study inclusion/exclusion criteria such as new onset of seizures, development of epilepsy, changes in motor function, and development of long-lasting symptoms potentially relating to tDCS.

We are also collecting information regarding the pregnancy status of participants as it is crucial for our research and subsequent follow-up visits. Understanding the pregnancy status is important due to the wide-ranging effects that pregnancy can have on the physiological and anatomical systems, including its impact on motor function. By identifying if participants are pregnant, we can accurately analyze and interpret their medical status since participation in the primary study. This knowledge will enable us to account for any potential influences that pregnancy may have on the outcomes and ensure that our analysis is comprehensive and accurate.

10.2.7.2 *Motor Assessments – Box and Blocks Test*

At the 6-month/12-month timepoint, we will administer the Box and Blocks test. We will send the necessary supplies to the participant and provide them with instructions over videoconference call. Participants will return Box and Blocks in the same packaging with a return label. The test will consist of one trial period followed by four tests, with two tests for each hand (dominant and non-dominant).

10.2.7.3 *Survey(s)*

10.3 Screening and Enrollment

The Screening and Enrollment visits and procedures are described in detail below.

After all questions have been answered and if no exclusion criteria are found during the prescreening call, the study team member will ask if the caregiver/legal guardian and/or adult child participant are interested in proceeding to the next step for further screening for inclusion/exclusion criteria. A Health Insurance Portability and Accountability Act (HIPAA) consent for a standardized medical record release is obtained in order to perform a medical record review. We will gather a medical record with current medical status to confirm inclusions and exclusion criteria are met. Information for all subjects will be collected and managed in accordance with HIPAA policies. This review is completed by the study

physicians for review of inclusion/exclusion by history and MRI/CT radiographic reports of the brain. Eligibility will be verified by the principal investigator after this review. The medical director will confirm participant eligibility in the study.

If a participant is excluded or declines participation, parents/guardians and/or adult child participant will be asked if they would like to have their contact information retained for future studies and/or to receive biannual lab newsletters. If yes, contact information will be kept separately from screening data. The parent/guardian and/or adult child participant will be notified of the information to be kept, including child name, child date of birth, child diagnosis, parent name, and parent contact information (phone number, email address and/or address).

Ineligible screening data will be stored until the close of enrollment to prevent re-contacting parents/legal guardians and/or adult child participants after screening. Once enrollment is completed, identifiers will be destroyed. De-identified screening information will be used to describe and analyze the recruitment process. The data will be stored securely in our HIPAA-compliant database to prevent unauthorized use of the information. This database will be accessible to a select number of study team members.

